8.4.1.7 Overall Survival (OS)

Overall survival is defined as the time from randomization to death from any cause. Subjects who are alive will be censored at the last known alive date. The last known alive date will be determined by selecting the last available date of the following study procedures: randomization, start date of adverse event, bone marrow collection, disease assessment, spleen assessment, vital signs assessment, electrocardiogram assessment, clinical laboratory collection, study drug administration, start date of concomitant or post-treatment medicine or procedure, survival follow-up, biospecimen sample collection, quality of life assessments, and performance status.

Overall survival will be analyzed using the statistical method described for time-to-event variables in Section 8.1.

8.4.1.8 Leukemia-Free Survival (LFS)

Leukemia-free survival is defined as the time from randomization to leukemic transformation ($\geq 20\%$ blasts) by bone marrow blasts or peripheral blood blasts per IWG criteria, or death from any cause, whichever occurs earlier, on or prior to the start of post-study treatment. Subjects who do not have leukemic transformation and are alive will be censored at the date of the last adequate peripheral blood blast assessment or bone marrow assessment on or prior to the start of post-study treatment. Subjects who are alive and without any hematology laboratory assessment for blast or bone marrow assessment will be censored at the date of randomization.

Leukemia-free survival will be analyzed using the statistical method described for time-to-event variables in Section 8.1.

8.4.1.9 Duration of SVR₃₅

Duration of SVR₃₅ is defined as the time from the first date of SVR₃₅ to the first assessment where SVR₃₅ is not maintained and the spleen volume is $\geq 25\%$ increase from nadir (the lowest spleen volume in the previous assessments), confirmed relapse or leukemic transformation per IWG criteria, whichever is earlier. Subjects without the

defined events will be censored at the date of the last spleen volume assessment, the last disease assessment, the last bone marrow assessment, or the last hematology lab test, whichever occurs the latest and on or prior to the start of the post-study treatment.

The distribution of duration of SVR₃₅ will be estimated for each treatment arm using Kaplan-Meier methodology. Median duration of SVR₃₅ and the corresponding 95% confidence interval will be provided for each treatment arm. There will be no statistical comparison for duration of SVR₃₅.

Only subjects who achieve SVR₃₅ will be included in the analysis.

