7.3 Statistical Analyses for Efficacy

Primary Efficacy Analysis

Analysis of the primary endpoint SVR_{35W24} will be conducted by comparing the SVR_{35W24} rate (the proportion of subjects achieving SVR_{35} at Week 24), using the stratified Cochran-Mantel-Haenszel (CMH) test. The study is designed to test the null hypothesis:

H_0 : SVR_{35W24} rate in Arm A (navitoclax + ruxolitinib) = SVR_{35W24} rate in Arm B (placebo + ruxolitinib) against the alternative hypothesis H_1 : SVR_{35W24} rate in Arm A \neq SVR_{35W24} rate in Arm B.

The stratification factors for the stratified statistical analyses will be described in detail in the SAP.

The 95% confidence interval (CI) for SVR_{35W24} rate will be estimated for each treatment arm based on the exact binomial distribution. Subjects without spleen volume assessment at baseline or the Week 24 timepoint will be treated as non-responders. Details of this analysis will be provided in the SAP.

Secondary Efficacy Analyses

The following secondary endpoints will be analyzed:

- Response rate endpoints: SVR_{35} , anemia response, reduction in grade of bone marrow fibrosis from baseline as measured by the European consensus grading system
- Continuous endpoints: Change in TSS at Week 24 from baseline, as measured by MFSAF v4.0; change in fatigue at Week 24 from baseline, as measured by the PROMIS Fatigue SF 7a; change in physical functioning at Week 24 from baseline, as measured by EORTC QLQ-C30 v3.0
- Time to event endpoints: Duration of SVR_{35} , OS, and LFS

Change in TSS at Week 24 from baseline is defined as the change in total symptom score at Week 24 from baseline, as measured by MFSAF v4.0.

SVR_{35} rate is defined as the proportion of subjects who achieve at least 35% reduction in spleen volume from baseline (SVR_{35}) at any time during the study.

Duration of SVR_{35} is defined as time from the first achievement of SVR_{35} to the first assessment where the spleen volume is less than 35% reduction from baseline and is at least 25% increase from the nadir (the lowest spleen volume).

Change in fatigue at Week 24 from baseline is defined as the change in fatigue score at Week 24 from baseline, measured by PROMIS Cancer Fatigue SF 7a.

Change in physical functioning at Week 24 from baseline is defined as the change in physical functioning score at Week 24 from baseline, as measured by EORTC QLQ-C30.

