8.2 Handling of Missing Data

Unless otherwise specified, missing data will be analyzed using the following methods for the efficacy analyses:

- Binary variables: If a subject does not have evaluation during a specific visit window, the subject will be considered a non-responder for that visit.
- Continuous variables: Mixed-effect Model Repeat Measurement (MMRM) will be used as the primary approach for handling missing data. Parameter estimation in linear mixed effects models will be based on the assumption of data being missing at random and the method of restrictive maximum likelihood (REML).
- Time-to-event variables: The time-to-event analysis will be based on observed data and will not impute values for missing evaluations. Subjects who do not have the event of interest will be censored at the censoring date defined for the respective endpoint in Section 8.3, Section 8.4 and Section 8.5.

Tipping Point Analysis for Binary Variables

The tipping point analyses will be performed to assess the robustness of the primary analysis results for SVR_{35W24} and TSS_{50W24} under missing not at random assumptions. The tipping point analyses are two-dimensional (i.e., assumptions about the missing outcomes on the treatment arm and the placebo arm can vary independently). The response rate among those subjects with a missing response is assumed to be p_0 for the control arm and p_1 for the treatment arm, and the response rate p_0 and p_1 systematically vary from 0% to 100% by every 10%, respectively. Given a set of (p_0, p_1) , the subjects with a missing response will be randomly assigned as responders or non-responders using

binomial distribution to generate 30 imputed datasets, and the same CMH method used for the primary analysis will be performed on each of the multiple imputed datasets to obtain the results for each comparison of the treatment arm versus the control arm. These results will then be aggregated using Rubin's method.

If one pair of shift parameters is found to just reverse the study conclusion (two-sided p -value > 0.05), then the shift parameters are identified as the tipping point. The results for a grid of shift parameter combinations are tabulated.

Tipping Point Analysis for Continuous Variables

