TSS response rate at any time during the study is defined as proportion of subjects who achieved change in TSS score from baseline \leq MCT at any time during the study. The MCT, derived using anchor-based analyses, has been determined to be at least 10 points for improvement in TSS from baseline. The validation of MCT of -10 is described in the Psychometric Analysis Report. TSS scores obtained after confirmed disease progression or start of post-study treatment will not be included in the analysis of TSS response rate. Subjects who do not have any TSS score after randomization will be treated as non-responders. Subjects who do not receive any study drug will be treated as non-responders. TSS response rate will be analyzed using the statistical method described for binary variables in Section 8.1. Similar analyses will be performed for TSS response rate at Week 24. The maximum reduction in TSS from baseline at any time will be summarized.

Time to TSS response is defined as the time from randomization to the first date of achieving TSS response based on MCT of at least 10 points. Time to first TSS response will be summarized descriptively for each treatment arm.

Duration of TSS response is defined as the time from the first date of achieving TSS response to the first date of loss of TSS response. Loss of TSS response is defined as diminishment of TSS below MCT improvement of 10 points. Subjects who do not lose TSS response will be censored at the last TSS assessment. Subjects with ≥ 2 consecutive missing TSS scores prior to losing TSS response will be censored at the last non-missing TSS assessment prior to losing TSS response. The distribution of duration of TSS response will be estimated for each treatment arm using Kaplan-Meier methodology. Median duration of TSS response and the corresponding 95% confidence interval will be provided for each treatment arm. Only subjects who achieve TSS response at any time will be included in the analysis of duration of TSS response. Sensitivity analysis of duration of TSS response may be performed by accounting for disease progression or death.

In addition, descriptive summaries of weekly TSS scores and individual symptom scores, change from baseline and percent change from baseline will be provided for each treatment arm. Change and percent change in TSS scores and individual symptom scores from baseline at Week 24 may also be presented graphically for each treatment arm.

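### Duration of SVR35 ends at leukemic transformation or relapse but censors death, so its Kaplan-Meier median does not describe time alive and in response

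*SAP*

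**What the plan says.** SAP 8.4.1.9 starts the clock at the first SVR35. It stops the clock at the earliest of three things: SVR35 no longer held with spleen volume at least 25% above its nadir, "confirmed relapse or leukemic transformation per IWG criteria, whichever is earlier". Subjects without one of these "defined events will be censored at the date of the last spleen volume assessment" or, if later, the last disease assessment, marrow assessment or hematology test, up to the start of post-study treatment. The section does not mention death; that deaths are censored follows from the event list and the censoring rule together.

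No general rule changes this. SAP 8.2 says: "Subjects who do not have the event of interest will be censored at the censoring date defined for the respective endpoint". Protocol 7.3 is narrower than the SAP. There the duration runs "to the first assessment where the spleen volume is less than 35% reduction from baseline and is at least 25% increase from the nadir", with no mention of relapse, transformation or death, and subjects without the event are censored at the last adequate assessment.

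The output is a Kaplan-Meier curve and a median with 95% CI per arm, among SVR35 responders only. The SAP adds: "There will be no statistical comparison for duration of" SVR35. The endpoint is in neither ranked list (Protocol 7.6; SAP 12.0, Table 1).

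**The concern.** A definition confined to spleen volume, with death censored, could be defended as a measure of how long the spleen effect lasts. The SAP does not use that definition. It ends the response at relapse or leukemic transformation even when the spleen is still reduced. Once disease failure outside the spleen counts, it is hard to see why death does not: a responder who transforms has an event, while one who dies first is handled as though the response might have continued.

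The protocol's clinical hypothesis includes more durable spleen responses, and duration of response is part of a secondary objective. The two medians will be read side by side even without a test. If responders in one arm die more often before any listed event, the medians as defined would not show it.

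**Working it through.** **Inputs.** Neither document gives a median duration, a loss rate or a death rate among responders, and the OS event counts and hazard ratio are blacked out. There is no planned figure to reproduce, and all rates below are assumptions.

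**How death is handled elsewhere in the SAP.**

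| Endpoint | Death |
|---|---|
| LFS (8.4.1.8), PFS (8.5.4) | event |
| Duration of SVR35 (8.4.1.9) | censored; no sensitivity analysis |
| Duration of TSS50 (8.4.1.1) | censored; no sensitivity analysis |
| Duration of TSS response (8.4.1.1) | censored; optional sensitivity analysis |

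**Formula.** Let L be the hazard of a listed event (loss) and D the hazard of death in response, both constant and independent.

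- Median with deaths censored (SAP rule): ln 2 / L
- Median time alive and in response: ln 2 / (L + D)
- Relative excess of the first over the second: (L + D)/L − 1 = D/L

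**Corners of the assumed range** (L 0.20 to 0.30 per year, D 0.05 to 0.15 per year):

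| L | D | SAP rule, years | Death as event, years | Excess |
|---|---|---|---|---|
| 0.30 | 0.05 | 0.693/0.30 = 2.31 | 0.693/0.35 = 1.98 | 17% |
| 0.30 | 0.15 | 2.31 | 0.693/0.45 = 1.54 | 50% |
| 0.20 | 0.05 | 0.693/0.20 = 3.47 | 0.693/0.25 = 2.77 | 25% |
| 0.20 | 0.15 | 3.47 | 0.693/0.35 = 1.98 | 75% |

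The excess runs from 17% to 75%. If D = 0 it is zero.

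**Difference between arms.** Take equal loss of 0.30 per year, with death in response at 0.15 per year in one arm and 0.05 in the other. The SAP rule gives 2.31 years in both arms. Time alive and in response has medians of 1.54 and 1.98 years. The threefold contrast is chosen only to show the mechanism.

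**Kaplan-Meier check.** This simulation assumes assessments every 12 weeks and 24 to 60 months of follow-up. With 20,000 responders and an assumed true median time to loss of 24 months, the SAP rule gives 24.9 months. Counting death gives 24.9, 22.1, 19.3 and 16.6 months at annual mortality in response of 2%, 5%, 10% and 15%. The tie at 2% arises because events fall mostly on the visit grid.

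In 1,000 simulated arms of 60 responders (an assumed number) for each of three settings, the SAP median was never the shorter one. It was strictly longer in 83% of arms (24 months, 5% mortality), 97% (24 months, 10%) and 91% (36 months, 5%).

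**Dependence on the target.** With a 24-month median to loss and 5% annual mortality, the monthly hazards are ln 2/24 = 0.0289 and −ln(0.95)/12 = 0.0043. Three targets give three answers:

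- deaths censored: 24 months
- loss or death: ln 2/0.0332 = 20.9 months
- cumulative incidence of loss, with death competing, reaches 50% at 25.7 months

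The SAP median is longer than the second and shorter than the third.

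**The case against.** A reader might infer that the SAP median is simply biased upward. The documents do not support that. Neither states an estimand for this endpoint, and Protocol 7.3 defines it by spleen volume alone. For spleen-response duration with death as independent censoring, the Kaplan-Meier median is a recognised estimate, and against cumulative incidence of loss the direction reverses. The claim holds only against time alive and in response.

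The rates are also unsupported. OS powering counts all deaths, including those in non-responders, after loss of response and after post-study treatment, so it does not show how many responders die in response. Scheduled on-treatment scans end at Week 97, which is 84 weeks (about 1.6 years) after a first response at Week 13. The illustrated SAP medians of 2.3 to 3.5 years lie beyond that, where scans remain only at treatment completion and post-treatment visits. The percentages are therefore not a forecast for this trial.

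The consistency argument cuts both ways. Both TSS durations also censor death in their main analysis, and the only concession is optional: "Sensitivity analysis of duration of TSS response may be performed by accounting for disease progression or death". Consistency among the response durations supports a sensitivity analysis more clearly than a new main definition. Nor are deaths hidden overall: they count in OS, LFS and PFS and appear by arm in the safety overview (SAP 9.2.2).

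All of this stands, and it limits the point. It does not explain why transformation and relapse end a response while death does not, or why no analysis of this endpoint accounts for death. Survival endpoints in all randomized subjects do not show how many responders died while still in response.

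**Conclusion.** The gap is real and modest. SAP 8.4.1.9 combines spleen and non-spleen failures, omits death and states no estimand, so the reported median will not describe time alive and in response. Relative to that quantity it cannot be shorter. The excess is 17% to 75% over the assumed hazards, which rest on constant and independent rates that the documents do not supply, and nil if no responder dies in response.

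A reader might go further and infer that a trial conclusion or the type I error rate is at risk, or that one arm is favoured. Neither inference is supported: the endpoint is descriptive and outside the testing sequence, and nothing in the documents indicates how deaths among responders will divide between the arms. What is at stake is the reading of the two medians as evidence of durability.

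**What to change.** In SAP 8.4.1.9, prespecify an analysis of duration of SVR35 in which death from any cause, on or before the start of post-study treatment, is an event on the date of death.

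- **Preferred:** make this the main definition, because the event list already goes beyond the spleen, and keep the death-censored version as a sensitivity analysis. Making it the main definition is open to debate.
- **Minimum:** keep the present definition, state the estimand it targets, and add the death-as-event version as a sensitivity analysis.
- **In either case:** report by arm the number of responders who die without another listed event.

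Reconcile the SAP event list with the spleen-only definition in Protocol 7.3.

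**Cost.** No new data are needed, since death dates are already collected for OS, and the extra analysis work is small. Reported durations may become somewhat shorter. Any change to the protocol text needs IEC/IRB approval (Protocol 8.1) across approximately 190 sites in 26 countries. The SAP change can be made first, with the difference from Protocol 7.3 stated there until the protocol is next amended.

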Anemia response rate is defined as the proportion of subjects who achieve anemia response at any time during the study.

Overall survival is defined as time from randomization to death from any cause.

Leukemia-free survival is defined as time from randomization to leukemic transformation ($\geq 20\%$ blasts) by bone marrow blasts or peripheral blood blasts per IWG criteria, or death from any cause, whichever occurs earlier.

Rate of reduction in grade of bone marrow fibrosis is defined as the proportion of subjects who achieve reduction of at least 1 grade in bone marrow fibrosis measured by the European consensus grading system.

Unless otherwise specified, all response rate secondary endpoints will be analyzed using the stratified CMH test. The point estimate and 95% CIs based on the exact binomial distribution will be presented for each treatment arm. Unless otherwise specified, subjects with missing data for a visit will be treated as non-responders for that visit.

Unless otherwise specified, all time to event secondary endpoints will be analyzed by using stratified log-rank test. Subjects who do not experience the event of interest will be censored at the last adequate assessment. The hazard ratio (HR) for treatment effect and the corresponding 95% CI will be estimated using stratified Cox proportional hazards model. In addition, survivorship functions will be estimated by using Kaplan-Meier product-limit method. Estimated survival curves will be presented.

Unless otherwise specified, all continuous patient-reported outcome endpoints will be analyzed using the linear mixed effects model. Subjects with missing data will be handled by the missing at random assumption within the framework of the linear mixed effects model.

Statistical analyses of secondary endpoints will be described in detail in the SAP.

Additional Efficacy Analyses

Details of additional efficacy analyses will be provided in the SAP. Additional supportive efficacy statistical analyses may be performed if deemed necessary and helpful in understanding the drug effect.

Subgroup Analysis for Efficacy

Supportive subgroup analyses, such as platelet count and DIPSS+, will be performed for the primary endpoint. Details of subgroup analyses will be provided in the SAP.

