APPENDIX D. ACTIVITY SCHEDULE

The following table shows the required activities. The individual activities are described in detail in the **Operations Manual**.

Study Activities Table

Activity	Screening/ Baseline	Week 1	Week 1	Week 2	Week 3	Week 5	Week 7	Week 9	Week 13, 17, 21, 25	Q12 weeks as of Week 37	Treatment Completion Visit	30-Day Safety Visit (± 3 Days)	Post-Treatment Visits (± 3 Weeks)	Survival Follow Up
	Day -28 to Day -1	Day 1	Day 2	Day 1 (± 1 day)	Week 13, 17, 21 Day 1 (± 2 days). Week 25 Day 1 (± 3 days)	From Week 37 Day 1 (± 4 days)								
INTERVIEWS & QUESTIONNAIRES														
Informed consent	✓													
Eligibility criteria	✓													
Medical/surgical/transfusion history	✓	✓												
Alcohol and nicotine use	✓													
Adverse event assessment	✓	✓	✓	✓	✓	✓	✓	✓	✓	✓	✓	✓		
Prior/concomitant therapy/transfusion	✓	✓	✓	✓	✓	✓	✓	✓	✓	✓	✓			
Post-treatment therapy/transfusion/surgery												✓	✓	✓
MFSAF v4.0 (Daily)	✓	✓ (Daily through end of Week 36)												
EORTC QLQ-C30 v3.0		✓				✓			✓ (Week 13, 25)	✓	✓			
PROMIS Fatigue SF 7a	✓	✓				✓			✓ (Week 13, 25)	✓	✓			
EQ-5D-5L		✓				✓			✓ (Week 13, 25)	✓	✓			
PGIC									✓ (Week 13, 25)					

Activity	Screening/ Baseline	Week 1	Week 1	Week 2	Week 3	Week 5	Week 7	Week 9	Week 13, 17, 21, 25	Q12 weeks as of Week 37	Treatment Completion Visit	30-Day Safety Visit (± 3 Days)	Post-Treatment Visits (± 3 Weeks)	Survival Follow Up
	Day -28 to Day -1	Day 1	Day 2	Day 1 (± 1 day)	Week 13, 17, 21 Day 1 (± 2 days). Week 25 Day 1 (± 3 days)	From Week 37 Day 1 (± 4 days)								
PGIS	✓	✓							✓ (Week 13, 25)					
ECOG performance status	✓	✓		✓	✓	✓	✓	✓	✓	✓	✓			
Survival follow-up call (approximately every 2 months for up to 8 years)														✓
LOCAL LABS & EXAMS														
MRI (or CT scan) for spleen assessment	✓								✓ (Week 13, 25)	✓ (Week 37, 49, 73, 97)	✓		✓	
12-lead ECG	✓					✓					✓			
Vital signs: including height (Screening only), weight, BP, pulse, and body temperature	✓	✓		✓	✓	✓	✓	✓	✓	✓	✓	✓		
Physical examination including skin examination, spleen and liver measurement by palpation	✓	✓		✓	✓	✓	✓	✓	✓	✓	✓		✓	
Disease Assessment by IWG									✓ (Week 13, 25)	✓ (Week 37, 49, 73, 97)	✓		✓	
Serum/urine pregnancy test	✓	✓				✓		✓	✓ (monthly from Week 25 where a	✓ (monthly where a regulatory requirement)	✓			

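### Duration of SVR35: scheduled on-treatment spleen scans end at Week 97 but blood counts keep responders at risk, so the late curve can be overstated; the SAP event also differs from the protocol's

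*SAP*

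**What the plan says.** **SAP 8.4.1.9.** Duration runs from first SVR35 to the first assessment at which SVR35 is no longer held and volume is up at least 25% from nadir, or to "confirmed relapse or leukemic transformation per IWG criteria, whichever is earlier". Responders without an event are censored at "the last spleen volume assessment, the last disease assessment, the last bone marrow assessment, or the last hematology lab test, whichever occurs the latest", no later than the start of post-study treatment. Each arm gets a Kaplan-Meier curve and a median. "There will be no statistical comparison for duration of" SVR35.

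**Protocol 7.3.** The event is spleen volume only: "the first assessment where the spleen volume is less than 35% reduction from baseline and is at least 25% increase from the nadir". For time-to-event secondary endpoints in general: "Subjects who do not experience the event of interest will be censored at the last adequate assessment". Detail is left to the SAP.

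**Protocol Appendix D.**
- "MRI (or CT scan) for spleen assessment": screening, Weeks 13, 25, 37, 49, 73 and 97, the treatment completion visit and post-treatment visits.
- "Disease Assessment by IWG": the same post-baseline times.
- Bone marrow: the last scheduled on-treatment sample is at Week 73.
- Haematology: every 12-weekly visit from Week 37, with no last week given.
- "Physical examination including skin examination, spleen and liver measurement by palpation": also every 12-weekly visit.

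Treatment itself is open-ended (Protocol 4.1 and 5.5).

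**The concern.** A subject counted at risk at time t should be one whose event would have been seen had it happened by t. A blood count meets that test for leukemic transformation. It does not for spleen loss, which under the SAP shows only on MRI or CT. After Week 97, a loss in a responder who stays on treatment is dated late, at the next scan whenever that comes, or is missed if the data cut comes first. Both push the curve up.

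The SAP's neighbouring endpoints are censored on dates that bear on their own events: duration of TSS50 at the last TSS assessment (8.4.1.1), LFS at the last blast or marrow assessment (8.4.1.8) and PFS at the last adequate disease assessment (8.5.4).

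Duration of SVR35 is a named secondary endpoint, and more durable response is part of the clinical hypothesis (Protocol 2.1). A long median could be read as scan-confirmed when few scans lie behind it. Separately, protocol and SAP define two different quantities under one name.

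**Working it through.** Neither document gives an expected duration or event count for this endpoint, so there is no planned figure to reproduce.

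**1. Schedule arithmetic (Appendix D).** Longest duration supported by scheduled on-treatment scans = 97 − week of first SVR35: 97 − 13 = 84, 97 − 25 = 72, 97 − 37 = 60 weeks. The next haematology visits are Weeks 109, 121 and 133. They carry a Week 13 responder to 96, 108 and 120 weeks with no new scheduled scan. Before Week 97, blood counts outrun scans by at most 12 weeks (Week 61 after the Week 49 scan, Week 85 after the Week 73 scan).

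**2. Direction.** Simulation of 20,000 responders. Assumptions, not in the documents: exponential spleen loss with median 96 weeks, so true S(t) = 0.5^(t/96); first response at Week 13/25/37 in 70/25/5%; data cut uniform over Weeks 110 to 220; spleen loss the only event, seen only at a scan.

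| Weeks | True | SAP rule, no off-treatment scan | SAP rule, stopping unrelated to loss (median 150 weeks), completion scan |
|---|---|---|---|
| 84 | 0.545 | 0.562 | 0.542 |
| 108 | 0.459 | 0.562 | 0.536 |
| 132 | 0.386 | 0.562 | 0.523 |

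The estimate is close at 84 weeks and then goes flat, or nearly so.

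**3. Size depends on what follows a loss.** Second simulation, 40,000 responders per case. Assumptions: first response at Week 13/25/37 in 50/40/10%; transformation 3% per year; entry over 100 weeks; cutoff 156 weeks after last entry; other stopping 0.4% per week; completion scan made in 90%; 5% of scans missed; post-treatment visits in half of those who stop. With a true spleen median of 104 weeks, the composite hazard is ln 2/104 + 0.03/52 = 0.00724 per week, a true composite median of 96 weeks. Spleen medians of 75 and 150 give 71 and 133. Estimated composite medians under the SAP rule, in weeks:

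| After spleen loss | True spleen median 75 | 104 | 150 |
|---|---|---|---|
| No stopping, no prompted scan | 84 | 156 | 228 |
| Half stop, mean lag 26 weeks | 84 | 126 | 180 |
| All stop, mean lag 26 weeks | 84 | 113 | 156 |
| All stop, mean lag 8 weeks | 78 | 106 | 144 |
| None stop, 50% chance of a scan at each 12-weekly visit | 78 | 108 | 144 |
| Reference: 24-weekly scans continue (for calculation only, not a proposal) | 79–84 | 105–108 | 138–144 |

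At a true median of 104 weeks, the end of scans adds from about 0 (106 lies within 105–108) to 156 − 108 = 48 weeks. At 75 weeks it adds almost nothing.

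**4. Planned analysis times.** With cutoffs 24 or 48 weeks after last entry, the SAP rule gives 0.50–0.55 at 96 weeks against a true composite 0.50.

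**5. Would last-scan censoring be better?** Spleen-only event, true median 104, late cutoff, ten behaviour cases including the five above. True S(120) = 0.5^(120/104) = 0.45. The SAP rule gives 0.47–0.57 and last-scan censoring 0.38–0.50. With no stopping and no prompted scans both are too high (0.57 and 0.50); when the other assumptions were varied over 72 settings for that case, the two estimates enclosed the truth in none. At the early cutoffs, last-scan censoring gives 0.28–0.48 at 96 weeks against 0.53, with only 0.1–1.8 of 75 responders at risk. For scale, the sampling SD of the SAP-rule estimate at 120 weeks with 75 responders is about 0.06.

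**6. Scan support.** In the same late-cutoff cases, 22–27 of 75 responders are at risk at 120 weeks under the SAP rule, but only 7–12 have a scan at or after that time.

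**7. Event definitions.** The spleen component is the same in both documents. The SAP adds confirmed relapse and leukemic transformation. With the same follow-up, extra events can only shorten durations, so this difference works against the censoring effect.

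**The case against.** The case for leaving the SAP alone is substantial.

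- *Haematology is proper follow-up for transformation, which is in the composite.* This stands, and is why the rule should stay for the composite.
- *Losses will be found.* Palpation continues every 12 weeks, progression or lost benefit is a reason to stop, assessment at progression is recorded (Protocol 5.5), and the completion visit has a scan. SAP 8.1 also counts a single relapse as confirmed when it is the last response. The simulation carries relapse only through stopping and prompted scans, so its larger excesses are, if anything, too high. This limits the size but does not remove the gap. Protocol 5.5 lets subjects stay on treatment after progression, palpation is not an SAP event, and no supplied text says when a suspected loss after Week 97 is scanned.
- *Scans may continue.* The Operations Manual is not supplied. Appendix A defines an every-24-weeks abbreviation that the supplied text does not use, and Weeks 49, 73 and 97 are 24 weeks apart. With continued 24-weekly scans, both censoring rules give 0.45–0.47 at 120 weeks against 0.45. The manual could therefore settle the matter, but Appendix D presents its table as the required activities and stops scans at Week 97.
- *The wider event may be deliberate.* The protocol defers detail to the SAP, and its censoring sentence is a default. That is a fair explanation, but two definitions of one named endpoint remain.

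A reader might go further and infer that nothing past 84 weeks rests on a scan. The documents do not support that: completion and post-treatment scans are scheduled (Appendix D, Protocol 5.7). In the five cases of the table, 51–76% of responder-time past 84 weeks lay after the last scan, so 24–49% did not. For Week 25 or 37 responders, on the other hand, 84 weeks is too lenient.

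**Conclusion.** The point holds and is minor. The direction follows from the documents: the supplied schedule lets follow-up for spleen loss run past the scans that could show it, which can only delay or miss losses. The size does not follow from them. It is near zero if a loss promptly leads to stopping or a scan, small at the Week 24 and Week 48 analyses, and appreciable only with long responses and late follow-up.

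It would be tempting to conclude that the reported median will be too long by most of a year. The 48-week excess needs losses that lead to neither stopping nor a scan, and a cutoff 156 weeks after last entry that neither document sets. It would be equally wrong to conclude that the SAP rule should give way to last-scan censoring, or that the two together bound the truth: after Week 97 the scans that keep a subject in follow-up are themselves linked to stopping or suspected loss.

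No test, alpha or primary result depends on this endpoint. All simulated sizes rest on the stated assumptions; only the 84, 72 and 60 weeks and the event mismatch come straight from the documents.

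**What to change.** 1. Reconcile the event definition between Protocol 7.3 and SAP 8.4.1.9. If the composite is intended, say so in both.
2. Keep the current censoring rule for the composite. Add a spleen-only sensitivity analysis, censored at the last adequate spleen volume assessment on or before the start of post-study treatment. This matches the protocol's event and its default censoring. Report it as a sensitivity result, not as a bracket or bound.
3. Under the curve, show numbers at risk based on each subject's last spleen scan, counting completion and post-treatment scans. Report how many responders still on treatment after Week 97 had a later scan, since that shows how large the problem is. Mark the part of the curve with little scan support, so that a median there is not read as scan-confirmed. This is better than a fixed 84-week cut.

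Cost: a SAP text edit, a matching protocol clarification, one extra analysis and a figure footnote, with no new visits or data. The downside is that the median may look less favourable or be reported as not reached.
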